#### Management of DVT in the Trial

A Radiology Report Form should be completed for all Doppler ultrasounds and venograms. This form, and in the case where there is evidence of DVT, the best image, still or video, should be returned to the CLOTS Co-ordinating Centre in Edinburgh.

If a popliteal or femoral vein DVT is detected during the routine Doppler ultrasound examinations, the responsible clinician will need to decide whether to confirm the presence and extent of any thrombus using venography. Although they may only perform confirmatory venography where the Doppler ultrasound is equivocal in their normal practice, compared with treating patients with a swollen leg the positive predictive value of a screening Doppler ultrasound study performed in an asymptomatic patient is likely to be lower. Put another way, the Doppler result is more likely to produce a false positive result in an asymptomatic patient. If the clinician is satisfied that the patients has a DVT (with or without a confirmatory venogram) the patient should be anticoagulated using subcutaneous heparin according to local protocols as long as there is no contraindication (SIGN Guidelines 1999).

If only calf vein thrombus is detected (by screening Doppler ultrasound and/or venography), the responsible clinician may anticoagulate the patient according to local protocols or alternatively arrange a follow up Doppler ultrasound approximately seven days later to identify any propogation into the popliteal vein. If definite popliteal or femoral vein thrombus is detected the patient should be anticoagulated unless contraindicated. If calf vein thrombus is detected during the first scheduled scan (between Day 7 to 10) a scan should also be performed between Days 25 and 30 in addition to any other scans deemed necessary.

If a patient develops symptoms or signs suggestive of DVT during their admission they should be investigated by either Doppler ultrasound and/ or venography and treated according to local protocols if the diagnosis is confirmed. Such patients should still have a Doppler ultrasound between Day 25 and 30 blinded to treatment allocation.

#### Analyses

All analyses will be based on intention to treat.

#### **Primary Outcome**

Presence of first symptomatic or asymptomatic DVT in the popliteal or femoral veins detected on either of two routine Doppler ultrasound scans (performed at about 7-10 days and 25 - 30 days) or contrast venography within 30 days of randomisation.

#### Secondary Outcomes

*In hospital:* symptomatic or asymptomatic DVT in the popliteal or femoral veins detected on either a Doppler ultrasound scan or contrast venography within 30 days of randomisation; death within 30 days, symptomatic or asymptomatic below knee DVT, confirmed fatal or non-fatal PE, medical complications of GCS (e.g. skin necrosis) and compliance with allocated treatment.

At six months: death from any cause, place of residence, post discharge DVT, PE, post DVT syndrome, disability (modified Rankin), and health related quality of life (EuroQol). The later effects of DVT/PE (e.g. breathlessness, leg pain or swelling, poor stroke recovery) or the complications of GCS (skin ulceration, amputation, loss of mobility) may be diverse, so it seems sensible to include a measure of overall health related quality of life.

Symptomatic DVTs, which occurred within 30 days of randomisation, would be counted in the primary endpoint. However, because the detection of such symptomatic DVTs is not blinded and hence prone to ascertainment bias, an analysis excluding these symptomatic DVTs will also be performed. Inevitably, some patients will not survive to have both routine Doppler ultrasounds and many of these will not have a detailed autopsy to establish whether they had a DVT or PE prior to death. However, it is possible that there will be an imbalance in the number of such deaths between the treatment groups especially if GCS are very effective in preventing fatal PE. Therefore, we will also perform an analysis combining our primary outcome

with death within 30 days, that is of 'death or confirmed symptomatic or asymptomatic DVT on routine Doppler ultrasound or contrast venography by Day 30'.

#### Preplanned Subgroup Analyses

*Preplanned Subgroup Analyses include:* the effect of treatment allocation on the primary outcome subdivided by key baseline variables:

- Time from stroke onset to randomisation (Day 0 or 1 vs 2 to 10)
- Use of anti thrombotic agents (use of either heparin, warfarin or thrombolytic agent vs none)
- Paralysis of leg (complete vs. incomplete)
- Unaffected leg (as model for immobile medical patient)

The proportion with a primary or secondary outcome will be compared using odds ratios with 95% confidence intervals. Results will be adjusted for any imbalance in baseline variables.

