#### **Randomisation Procedure**

The randomising clinician or nurse collects baseline data necessary to complete a randomisation form. He/she then rings a telephone randomisation service, giving the baseline data (which are then stored securely) and receives the treatment allocation at the end of the call. A minimisation program is used to achieve optimum balance for important prognostic factors i.e.

- Delay since stroke onset. (Day 0 or 1 vs. Day 2-10)
- Stroke severity (using a validated prognostic model (Counsell 1996) which includes the following factors; age, pre stroke dependency in activities of daily living, living with another person prior to stroke, able to talk and orientated in time, place and person, and able to lift both arms to horizontal position against gravity).
- Severity of leg paresis (able or not to lift leg off the bed)
- Use of heparin, warfarin or thrombolysis (rt-PA) at the time of enrolment
- Centre

By balancing randomisation within centres we should avoid problems associated with variation in accuracy of Doppler ultrasound between centres.

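### The protocol lets observed baseline imbalance choose the covariates of the primary odds ratio, a rule that tends to leave out the minimisation factors

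*Protocol*

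**What the plan says.** Under Randomisation Procedure the protocol states: "A minimisation program is used to achieve optimum balance for important prognostic factors". Five factors follow: delay since onset, stroke severity from a prognostic model, leg paresis, use of heparin, warfarin or rt-PA at entry, and centre. The section adds that balancing within centres should deal with differences in ultrasound accuracy between them.

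The section Analyses says only that analysis is by intention to treat. The effect measure appears at the end of Preplanned Subgroup Analyses: "The proportion with a primary or secondary outcome will be compared using odds ratios with 95% confidence intervals". The next and last sentence is "Results will be adjusted for any imbalance in baseline variables". No other sentence in the protocol deals with covariate adjustment. Delay, antithrombotic use and leg paralysis reappear there, but only as subgroup variables.

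**The concern.** The adjustment sentence follows one that covers all primary and secondary outcomes, so it governs the main odds ratio of each trial despite the subgroup heading. Two things are badly fixed.

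First, the covariate set is decided by the data. With imbalance undefined, two analysts could follow the same sentence and report different odds ratios.

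Second, the trigger works against the allocation method. Minimisation holds its factors close to balance, so they seldom qualify for adjustment, although the protocol itself regards them as prognostic. Balance on a prognostic factor reduces the real variability of the estimate. A model that omits the factor does not know this, so its standard error tends to be too large. Variables outside the minimisation enter only when chance makes them look unequal.

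At stake are a single pre-defined primary estimate, correctly sized intervals and, if the factors are strong, some power.

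**Working it through.** **1. The plan's own figures.** Stated inputs (Sample Size): 15% v 9% in Trial 1, 13% v 9% in Trial 2, 90% power, 8% deaths plus 8% missing scans. Assumed: two-sided 5%, 1:1 allocation.

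n per arm = [1.96·√(2p̄(1−p̄)) + 1.2816·√(p₁(1−p₁) + p₂(1−p₂))]² / (p₁−p₂)²

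- Trial 1: (0.9007 + 0.5865)² / 0.06² gives 615 per arm, 1230 in all; 1230/0.84 gives 1465, against 1500 stated.
- Trial 2: (0.8673 + 0.5659)² / 0.04² gives 1284 per arm, 2568 in all; 2568/0.84 gives 3058, against 3000 stated.

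The enrolment figures match an unadjusted comparison of two proportions, so they do not depend on the adjustment rule.

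**2. How many variables could trigger adjustment.** The randomisation forms carry 19 numbered items.

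- Items 1, 2, 4, 5, 6, 8, 16, 17 and 18 feed the minimisation factors.
- Item 19 asks whether a second scan is practical.
- Item 3 (walking unaided) is nearly fixed by the inclusion criterion.
- This leaves items 7 and 9 to 15 plus sex, which is 9 variables, or 10 with item 3.

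If they were independent and each tested at 5%, the chance that at least one looks imbalanced is 1 − 0.95⁹ = 37% or 1 − 0.95¹⁰ = 40%. At a 10% threshold it is 1 − 0.9⁹ = 61% or 1 − 0.9¹⁰ = 65%. The protocol sets no threshold.

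**3. Effect on the test and interval.** Simulation under the null with 1500 patients, minimisation on four binary factors (80% biased coin), eight other baseline variables of which four were prognostic, and an imbalance trigger of p<0.10. There were 2500 runs per setting; the Monte Carlo SE at 5% is √(0.05·0.95/2500) = 0.4 points. Every prognostic factor has the odds ratio shown. All of these settings are assumptions.

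| Null rejection | OR 1.5 | OR 2 | OR 3 |
|---|---|---|---|
| Unadjusted | 5.4% | 4.4% | 3.6% |
| Imbalance-triggered | 5.2% | 4.3% | 3.3% |
| Minimisation factors pre-specified | 5.4% | 4.6% | 4.6% |
| Most favourable model, picked afterwards | 6.1% | 5.9% | 6.7% |

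The triggered rule behaves much like no adjustment. Mean model SE over empirical SD for the triggered rule is 0.1606/0.1627 = 0.99, 0.1511/0.1456 = 1.04 and 0.1383/0.1275 = 1.08 across the three columns. For the pre-specified model at OR 3 it is 0.1456/0.1434 = 1.02. Each SE should be compared with its own SD, because the adjusted log odds ratio is on a different (conditional) scale.

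**4. Effect on the estimate and power.** With a true conditional odds ratio of (0.09/0.91)/(0.15/0.85) = 0.56 and prognostic odds ratios of 2 (1500 runs), the mean log odds ratio and power were:

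- unadjusted: −0.542 (OR 0.58), 90.0%
- triggered: −0.545 (OR 0.58), 90.7%
- minimisation factors: −0.566 (OR 0.57), 90.7%
- most favourable model: −0.601 (OR 0.55), 92.9%

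Centre was not in this simulation. A smaller one (500 runs, 1680 patients, 20 centres with SD 0.6 to 1.0, leg paresis OR 2.5, other factors weaker, treatment OR 0.575, all assumed) gave power of 72% unadjusted v 74% adjusted in one scenario and 75% v 80% in the other, with a Monte Carlo SE of about 2 points. It did not test the trigger. Its null rejection of 3.6% and 3.8% lies within noise (SE about 1 point), so it is indicative only.

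**The case against.** The strongest defence is that covariate lists and model form are normally left to the SAP, which is not available here and may name the minimisation factors. The sentence also does not say that adjustment is confined to imbalanced variables, and it could mean an adjusted result supplied in addition to a plain odds ratio. Part of this stands: silence about the factors would be no fault, and a reader who infers that the protocol forbids them goes beyond the text. But the protocol is not silent. It states a rule that makes adjustment follow observed imbalance and does not label it supportive. An SAP that fixed covariates in advance would have to override it.

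A second defence is that the effect is small and mostly conservative. That also stands, and it limits the verdict.

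A third is that the trial has safeguards: scans for the primary outcome are read blind, and the steering committee and collaborators do not see interim results. These reduce the scope for choosing a model on the results. They do not supply a covariate list.

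A reader might also infer an inconsistency because minimisation splits leg paresis by ability to lift the leg while the subgroup splits complete from incomplete paralysis. The documents do not support that as an error. The randomisation forms record both leg lift and a flicker of movement for each leg, so the second cut is collected at baseline, and a subgroup need not copy a minimisation cut.

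**Conclusion.** The point holds in a limited form. The covariates of the primary odds ratio are tied to undefined, observed imbalance, and the rule tends to miss the factors used to allocate patients.

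The size depends on prognostic strengths that the protocol does not give. With odds ratios of about 1.5 to 2 there is little or no interval error. With odds ratios of about 3, intervals are about 8% too wide, null rejection falls to about 3.3%, and some power is probably lost, though the power evidence is thin. The estimate itself moves only slightly with the covariate set (0.55 to 0.58 in the case shown).

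A reader might infer that the rule inflates the type I error. The figures support that only if the model is picked after the results are seen (5.9% to 6.7%), and the protocol does not provide for such a choice. A reader might also count every item on the form as a possible trigger; only nine or ten lie outside the minimisation inputs.

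This is a change worth making, not a threat to the validity of either trial.

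**What to change.** Move the rule from the subgroup section to Analyses and replace the sentence with:

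> The primary analysis is a logistic regression of the primary outcome on allocation, adjusted for the minimisation factors (delay, predicted stroke severity, leg paresis, heparin/warfarin/rt-PA use, centre) whatever the observed balance, with small centres pooled or centre fitted as a random effect. The unadjusted odds ratio is reported alongside. Adjustment for other baseline variables because of observed imbalance is a labelled sensitivity analysis only.

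The leg-paralysis subgroup needs no change.

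The cost is a short text amendment. All the factors are collected at randomisation, and no stated sample size or event target changes. There are two small downsides: sparse centres need a handling rule, and the adjusted odds ratio is conditional, not marginal, so it will differ slightly from the crude one. Reporting both deals with the second.

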#### Sample Size

Ideally the trial would demonstrate the impact of graduated compression stockings on survival and functional status. However, this would require a trial of enormous sample size. We have therefore chosen a surrogate outcome as our primary outcome, i.e. presence of first symptomatic or asymptomatic DVT in the popliteal or femoral veins detected on either of two routine Doppler ultrasound scans (performed at about 7-10 days and 25 – 30 days) or contrast venography within 30 days of randomisation.

In this trial we have elected to define our sample size not in terms of the number of patients we plan to enrol but rather the number of primary outcomes we need to detect. To achieve at least 90% power in Trials 1 & 2 we need to identify about 175 and 300 patients with our primary outcome in each trial respectively. This might be achieved by enrolling 1500 and 3000 patients in Trials 1 and 2 respectively, if thrombus will be detectable in the popliteal or femoral veins within 30 days of randomisation in 15% of control patients, 9% of those wearing full length GCS and 13% of those wearing below knee stockings. If the current event rate in our pilot phase applies we may require about 2000 and 3500 in Trials 1 and 2 respectively.

The estimates of treatment effects are based on the systematic reviews and the prevalence of DVT detected on Doppler ultrasound in stroke patients estimated from a previous RCT (Muir et al 2000), an observational study (Oczkowski et al 1992) and our start up phase. A recent (Dec 2002) confidential review (by the trial statistician) of the event rates in the CLOTS start up phase(for all treatment groups combined) for the first 160 patients followed up to 30 days indicated that about 8% of patients had our primary outcome.

These sample sizes take into account: the uncertainty introduced by the 70% sensitivity and 97% specificity of Doppler ultrasound in identifying DVT in mainly asymptomatic patients; an attrition rate due to death (8% in our start up phase) and missing Doppler results (8% in our start up phase) in the first month; the anticipated low non – compliance rate.

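### At the quoted pilot rate of about 8%, the projected enrolment of about 2000 and 3500 does not yield the protocol's own targets of about 175 and 300 events

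*Protocol*

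**What the plan says.** All of this is in the Sample Size section of the protocol. The size of each trial is set "not in terms of the number of patients we plan to enrol but rather the number of primary outcomes we need to detect". The targets follow: "To achieve at least 90% power in Trials 1 & 2 we need to identify about 175 and 300 patients with our primary outcome".

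Two enrolment projections are then given. The first rests on planning rates: "This might be achieved by enrolling 1500 and 3000 patients in Trials 1 and 2 respectively", if popliteal or femoral thrombus is found "in 15% of control patients, 9% of those wearing full length GCS and 13% of those wearing below knee stockings". The second rests on the trial's own pilot data: "If the current event rate in our pilot phase applies we may require about 2000 and 3500 in Trials 1 and 2 respectively".

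The pilot rate comes from a confidential review of the first 160 patients with 30-day follow-up. That review, pooled over treatment groups, "indicated that about 8% of patients had our primary outcome". The section does not say whether patients who died or were not scanned are in the denominator. It adds that the sample sizes allow for, among other things, "an attrition rate due to death (8% in our start up phase) and missing Doppler results (8% in our start up phase".

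**The concern.** The section gives a target number of events, an event rate and an enrolment figure said to connect them. Multiplying rate by enrolment should return the target, and for the pilot-rate projection it does not. The section also says losses to death and missing scans have been allowed for, so the enrolment figure should if anything exceed the simple quotient of events over rate. It is below it.

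This is the only projection in the protocol that uses the trial's own event rate. A reader who takes it as the expected size will expect recruitment to finish too early. If recruitment were closed at those numbers, the event targets would be missed and the stated power might be too.

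**Working it through.** **Inputs from the protocol (Sample Size)**
- Event targets 175 and 300; power at least 90%.
- Planning rates 15% control, 9% full length, 13% below knee. Pooled rate: (15 + 9)/2 = 12% in Trial 1, (13 + 9)/2 = 11% in Trial 2. Risk ratio: 9/15 = 0.600 and 9/13 = 0.692.
- Enrolment 1500 and 3000 (planning rates), 2000 and 3500 (pilot rate).
- Pilot rate 8%, pooled over arms.
- Attrition 8% deaths plus 8% missing scans = 16%, so an evaluable fraction f = 0.84.

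**Assumed, because the section does not state them**
- Two-sided 5%, in line with the 95% confidence intervals planned for the analysis.
- 1:1 allocation.
- All rates are rates of detected DVT, so no further correction is made for the accuracy of Doppler.

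**Formulas**
- Events = N × f × pooled rate.
- Patients per arm: n = [1.96·√(2p̄(1−p̄)) + z·√(p1(1−p1) + p2(1−p2))]² / (p1−p2)², with z = 1.2816 for 90% power. For power at a given n, solve for z.

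**Step 1. Reproduce the planning-rate projection**

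For 90% power the formula gives 615 per arm (1230) in Trial 1 and 1284 per arm (2568) in Trial 2. Allowing for attrition, 1230/0.84 ≈ 1465 and 2568/0.84 ≈ 3058. So 1500 and 3000 are reproduced to within 3%, with attrition added on top of the planning rates. Power at those sizes after attrition is 90.7% and 89.5%.

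The events do not agree on that basis. Without attrition, 1500 × 0.12 = 180 and 3000 × 0.11 = 330, at or above target. With attrition, 1500 × 0.84 × 0.12 = 151 and 3000 × 0.84 × 0.11 = 277, below it. The enrolment figures include attrition, but the event targets are met only without it.

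**Step 2. Events from the pilot-rate projection**

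| | Trial 1 (N = 2000) | Trial 2 (N = 3500) |
|---|---|---|
| Target | 175 | 300 |
| 8%, no further attrition | 160 (9% short) | 280 (7% short) |
| 8.5%, no further attrition | 170 | 298 |
| 8%, f = 0.84 | 134 | 235 |
| Rate needed, no attrition | 175/2000 = 8.75% | 300/3500 = 8.57% |

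**Step 3. Enrolment needed for the event targets at 8%**
- 8% per enrolled patient: 175/0.08 = 2188 and 300/0.08 = 3750.
- 8% per evaluable patient: 2188/0.84 ≈ 2604 and 3750/0.84 ≈ 4464.

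**Step 4. Power if recruitment stopped at 2000 and 3500**

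A pooled 8% with the planned risk ratios gives arm rates of 0.16/1.600 = 10.0% v 6.0% in Trial 1, and 0.16/1.692 = 9.45% v 6.55% in Trial 2.

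| | Trial 1 | Trial 2 |
|---|---|---|
| No further attrition (1000 and 1750 per arm) | 91.0% | 88.8% |
| 16% attrition on top (840 and 1470 per arm) | 85.6% | 82.9% |
| Constant odds ratio, no further attrition | 93.1% | 90.6% |
| Constant odds ratio, 16% attrition on top | 88.4% | 85.2% |

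For 90% power at a pooled 8% and the planned risk ratios, 1930 and 3652 evaluable patients are needed, or 154 and 292 events. The Trial 1 target of 175 has room above that, which is why 160 events can still give 91%.

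**Step 5. Power if recruitment runs to the event targets**

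At a pooled 8%, 175 and 300 events correspond to 2188 and 3750 evaluable patients, with power of 93.2% and 90.7%.

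**The case against.** Several points on the other side have force.

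- The figures are hedged: about 8%, about 175 and 300, a size that may be required. The gap before attrition is only 7% to 9%. The count behind the 8% is not given. If it was 13 of 160, the exact 95% interval is 4.4% to 13.5%, and 175 events could need roughly 1300 to 3980 patients. No trial-specific rate is given either. This limits the precision of any projection but does not reconcile the printed figures: at 8.5% both yields are still below target. Fourteen of 160 (8.75%) would meet both targets, but it would normally be reported as 9%.
- The 8% may already be per enrolled patient, with deaths and unscanned patients in the denominator. Removing 16% again would then double count. This stands.
- Multiplying by 0.84 is a worst case. A DVT found on the first scan, or a symptomatic one, counts even if the patient later dies or misses the second scan.
- The design is event driven, so power is lost only if recruitment closes at the projected sizes. This stands and governs the severity.

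A reader might also infer that enrolment should have risen 1.5-fold and 1.375-fold, as the pooled rates fall from 12% and 11% to 8%. That ignores the margin in the planning-rate projection (180 events against 175, 330 against 300). Measured against the targets, the increases needed on the per-enrolled reading are 2188/1500 = 1.46 and 3750/3000 = 1.25, against 1.33 and 1.17 in the protocol.

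**Conclusion.** The pilot-rate enrolment figures miss the protocol's event targets at the rate the protocol quotes, on either reading of the denominator. They understate the enrolment needed by about 190 and 250 patients if the 8% is per enrolled patient. If it is per evaluable patient and all the stated attrition is additional, the understatement is about 600 and 960.

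Three stronger readings are not supported.
- That power is simply 86% and 83%. This needs the 8% to be per evaluable patient, the full 16% loss on top, and constant risk ratios. The denominator is not stated. On the per-enrolled reading, Trial 1 meets the 90% target and Trial 2 misses it by about one point.
- That 1500 and 3000 are underpowered. They give about 90% after attrition; what fails to match is their event yield.
- That funding or centre numbers rest on 2000 and 3500. The protocol text at hand does not say so, and it fixes the target in events.

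The severity is moderate: a wrong projection inside an event-driven design, which would keep its power if recruitment continued to the targets.

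**What to change.** Keep the event targets and the event-driven design. In the Sample Size section:

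1. State whether the pilot 8% is per enrolled or per evaluable patient.
2. Restate the pilot-rate enrolment as about 2200 and 3750 (per enrolled patient) or about 2600 and 4460 (per evaluable patient). Alternatively, keep 2000 and 3500 and state the events and power they deliver: 160 and 280 events with about 91% and 89% power, or about 134 and 235 events with about 86% and 83% power, according to the denominator.
3. Put the event targets and the 1500 and 3000 figures on the same attrition basis, noting that those sizes give about 91% and 89.5% power but about 151 and 277 events after 16% attrition.
4. State the significance level and allocation ratio used, so that the figures can be reproduced.

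The cost is a rewording of one section and a less favourable projected size or power. Nothing else in the design changes.

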**Doppler ultrasound** imaging provides a very accurate and specific tool to detect above knee thrombus in symptomatic patients. There is more uncertainty concerning its sensitivity and specificity for detecting calf vein thrombus and in asymptomatic patients (Davidson 1998). Reported sensitivities in asymptomatic patients vary between 42% and 70% with positive predictive values varying between 35% and 83% depending on the operator's expertise and the prevalence of DVT in the patient group examined. However, it is rapidly becoming the investigation of choice to confirm the diagnosis of DVT since it is non invasive (Baxter 1997). It is acceptable to patients, can easily be repeated several times and uses equipment which is widely available. Thus consent, accrual and compliance in a trial are likely to be more easily achieved than with alternatives.

**Plethysmography** This technique is of comparable accuracy to Doppler ultrasound and is also non invasive but it is not widely available in centres which are likely to participate in this randomised trial.

**Magnetic Resonance Imaging** Preliminary reports suggest that this technique might offer an alternative non invasive method of detection. However it is available in very few centres and has not yet been fully evaluated (Moody 1997, Kelly et al 2001).

**D-Dimers** are degradation products produced when thrombus present in the circulation is lysed. Raised levels of D-Dimers have been used as a very sensitive but less specific test for diagnosis of DVT (Bounameaux et al 1997). However, its performance in detecting DVT/PE in prevention studies remains to be established. At this time it could not be used as a test to confirm DVT, but given its sensitivity it might be used as a preliminary screening test to select patients for imaging (Harvey et al 1996, Bernardi et al 1998)

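### The 175 and 300 event targets are kept at the lower pilot event rate, where false-positive scans dilute the contrast: power at 8% is about 82–86% and 81–84%, not at least 90%

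*Protocol*

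**What the plan says.** All the relevant statements are in the protocol.

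- **Sample Size, basis.** The trial chooses to "define our sample size not in terms of the number of patients we plan to enrol but rather the number of primary outcomes" needed. "To achieve at least 90% power in Trials 1 & 2", the section says, "we need to identify about 175 and 300 patients with our primary outcome in each trial respectively".
- **Sample Size, design scenario.** "This might be achieved by enrolling 1500 and 3000 patients in Trials 1 and 2 respectively", if thrombus is detectable in 15% of control patients, 9% with full length stockings and 13% with below knee stockings.
- **Sample Size, pilot scenario.** About 8% of the first 160 patients, all treatment groups combined, had the primary outcome. At that rate enrolment might need to be about 2000 and 3500. No new event targets are given.
- **Sample Size, accuracy.** The sizes are said to allow for "the uncertainty introduced by the 70% sensitivity and 97% specificity of Doppler ultrasound in identifying DVT in mainly asymptomatic patients", for attrition (8% deaths, 8% missing scans) and for some non-compliance. No calculation is shown.
- **Detecting Deep Venous Thrombosis.** "Reported sensitivities in asymptomatic patients vary between 42% and 70% with positive predictive values varying between 35% and 83" per cent.
- **Primary Outcome and Management of DVT in the Trial.** A popliteal or femoral DVT on Doppler counts as an event. Confirmatory venography is left to the clinician.

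**The concern.** Fixing the number of events, rather than the number of patients, protects power against a low event rate only if the observed ratio between the arms does not depend on that rate. Imperfect specificity breaks this condition. False positives arise at nearly the same rate in both arms and do not shrink when true DVT becomes rarer. As the event rate falls they make up more of the total, the observed ratio moves toward 1, and each event carries less information about the stockings.

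The protocol supplies every element of the problem: 97% specificity, a pilot rate below the design rate, and event targets that do not change. If 175 and 300 events were reached at the pilot rate, recruitment could stop with less power than stated. A null result would then be harder to tell apart from dilution by false-positive scans.

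**Working it through.** **Inputs from the protocol:** detected rates 15%, 9% and 13%; 175 and 300 events; 1500 and 3000 patients, or 2000 and 3500 at the pilot rate; pilot rate 8%; sensitivity 70%, specificity 97%; attrition 8% + 8% = 16%.

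**Assumptions:** two-sided 5% test (no alpha is given for the sample size; the analysis uses 95% intervals), 1:1 allocation, 97% specificity per patient over the 30 days, and the pooled 8% applied to each trial.

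**Step 1. Reproduce the plan.** Patients per arm:

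n = [1.96√(2p̄(1−p̄)) + 1.2816√(p1(1−p1) + p2(1−p2))]² / (p1−p2)²

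- Trial 1, 15% v 9%: 1230 in total; 1230/0.84 gives 1465 (plan: 1500).
- Trial 2, 13% v 9%: 2568 in total; 2568/0.84 gives 3058 (plan: 3000).

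So the plan's enrolment follows from detected rates plus attrition. At the design rates, 175 and 300 events give 94.2% and 91.6% power, and the stated 90% holds.

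**Step 2. Separate true from false events.** detected = 0.70 × true + 0.03 × (1 − true), so true = (detected − 0.03)/0.67.

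- 15% → 17.9%, 9% → 9.0%, 13% → 14.9%. True risk ratios are 0.50 (Trial 1) and 0.60 (Trial 2).
- False share of events = 0.03 × (1 − true)/detected. At 12% detected it is 22%, at 11% it is 24%.
- At 8% detected, true = 7.46%, and the false share is 0.03 × 0.9254/0.08 = 34.7%. The implied positive predictive value of about 65% lies inside the range the protocol quotes.

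**Step 3. Lower the pooled detected rate to 8%, keeping the true effect constant.**

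| | Trial 1, constant RR | Trial 1, constant OR | Trial 2, constant RR | Trial 2, constant OR |
|---|---|---|---|---|
| True rates | 9.95% v 4.98% | 10.10% v 4.82% | 9.33% v 5.60% | 9.42% v 5.51% |
| Detected rates | 9.67% v 6.33% | 9.77% v 6.23% | 9.25% v 6.75% | 9.31% v 6.69% |
| Observed risk ratio (design 0.60; 0.69) | 0.655 | 0.638 | 0.730 | 0.719 |
| Power at 175 or 300 events | 82.0% | 86.3% | 80.6% | 84.1% |
| Events for 90% power | 222 | 197 | 396 | 360 |

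Power = Φ{[|p1−p2| − 1.96√(2p̄(1−p̄)/n)] / √([p1(1−p1) + p2(1−p2)]/n)}, with n = events/(2 × 0.08) per arm. For Trial 1 at constant RR, n = 175/0.16 = 1094 per arm, and Φ[(0.0333 − 0.0227)/0.0116] ≈ 0.82. Simulating 200,000 trials at constant RR gave 82.2% and 80.7%.

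**Step 4. Isolate the cause.** If the observed risk ratios stayed at 0.60 and 0.69 (no false positives), 175 and 300 events at 8% would give 93% and 91%. The loss therefore comes from specificity. Replacing 70% sensitivity by 42% leaves power at 82% and 81%.

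**Step 5. Vary the event rate.**

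- The protocol's own enrolment implies 175/2000 = 8.75% and 300/3500 = 8.57%. Power is 86% and 84% (constant RR).
- If the 8% is per enrolled patient, the rate among assessed patients is 0.08/0.84 = 9.5%. Power is 89% and 88% (constant RR) or 91% and 89% (constant OR).
- At 10%, power is 90.3% and 89.2% (constant RR).
- 8% of 160 is about 13 patients, with an exact 95% interval of about 4.4% to 13.5%.

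**The case against.** The strongest reply is that the size of the loss depends on choices the protocol leaves open.

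- **Effect scale.** The planned analysis uses odds ratios. Holding the true odds ratio constant gives 86% and 84%. This stands, so a range is reported.
- **Denominator.** The text does not settle whether the 8% is of all patients or of those with outcome data. The pilot enrolment figures fit the first better: 175/0.08 = 2188 and 300/0.08 = 3750 are nearer to 2000 and 3500 than the 2604 and 4464 needed after 16% attrition. Power would then be close to 90%. This stands too.
- **Precision.** The interval around 8% includes the design rates of 11–12%.
- **False-positive rate.** Symptomatic DVT and optional venography could bring the effective rate below 3%. At 8%, specificity of 98% gives 87% and 85%, and 99% gives 91% and 89% (constant RR). How far venography would help is unknown, since the protocol does not require it.

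The protocol's statement that accuracy is already allowed for does not answer the point. Targets set at 11–12% and carried unchanged to 8% cannot contain an effect that grows as the rate falls.

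Three stronger inferences are tempting but not supported:

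- A reader might take 15%, 9% and 13% as true rates, which would leave the planned enrolment badly underpowered. The section speaks of detectable thrombus and Doppler-detected prevalence, and Step 1 recovers the planned enrolment from that reading.
- A reader might apply 3% false positives independently to each of two scans, with a much larger loss. Nothing in the protocol supports independent errors on repeat scans of the same legs.
- A reader might think the Randomisation Procedure sentence, "By balancing randomisation within centres we should avoid problems associated with variation in accuracy of Doppler ultrasound between centres", is wrong. It concerns accuracy that differs between centres, and it does not claim to remove the average dilution.

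**Conclusion.** The point holds as an internal inconsistency: the stated power, the fixed event targets, the 97% specificity and the 8% pilot rate do not fit together. At the design rates the power statement is correct. At a detected rate of 8% among assessed patients, 175 and 300 events give about 82–86% and 81–84%. The shortfall is 4 to 8 points in Trial 1 and 6 to 9 in Trial 2, and it nearly vanishes if the assessed-patient rate is 9.5–10%.

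The direction follows from the protocol's own inputs. The size depends on the assumptions listed in the working, above all per-patient specificity and the denominator of the 8%. It should not be quoted as a single figure or as a loss already established by the pilot data.

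**What to change.** In the Sample Size section:

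1. State that 15%, 9% and 13% are Doppler-detected rates.
2. State whether 97% specificity is per scan or per patient.
3. State whether the 8% is of all patients followed or of those with outcome data.
4. Then do one of two things. Either recompute the event targets at the pilot rate with the false-positive rate among DVT-free patients held constant (at 8%, about 197–222 events for Trial 1 and 360–396 for Trial 2). Or keep 175 and 300 and give the power at the pilot rate as about 82–86% and 81–84%, with the assumptions.

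Leave the between-centre sentence in Randomisation Procedure as it is.

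The recalculation is short. Keeping the targets makes the stated power slightly less favourable. Raising them costs recruitment: at the upper end about 2780 and 4946 patients with outcome data, against 2188 and 3750 for 175 and 300 events at 8%.
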